Safety Outcome Measures

The safety outcome measures for this study are as follows:

- Adverse events and clinical laboratory abnormalities
- Vital signs, physical findings, ATAs, and clinical laboratory results during and following administration of MHAA4549A

Efficacy Outcome Measures

The primary outcome measure for this study is as follows:

- Time to normalization of respiratory function defined as:

– The time to cessation of O₂ support resulting in a stable SpO₂>95% for at least 24 hours
The secondary efficacy outcome measures for this study are as follows:

- Clinical failure after 24 hours post-infusion of study drug defined as:
 - Progression to increased O₂ requirement defined by an increase in oxygen supplementation from low flow oxygen (2–6 L/min) to high flow oxygen (> 6 L/min) or from oxygen supplementation alone to any PPV
 - Progression to ICU
 - Prolonged ventilation or O₂ support defined by > 2 weeks, or
 - Death
- Time to clinical normalization of vital signs (3/5 criteria must be met):
 - SpO₂>95% without supplemental O₂ for at least 24 hours
 - Respiratory rate < 24 breaths per minute without supplemental O₂ for at least 24 hours
 - Core temperature < 37.2°C immediately prior to receipt of any antipyretic drug, and at least 6-8 hours from the last dose of antipyretic or core temperature > 36°C in patients who are initially hypothermic
 - Heart rate (HR) < 100/minute
 - Systolic blood pressure (SBP) > 90 mmHg
- All-cause mortality at Day 14, Day 30, and Day 60
- Influenza A viral load in nasopharyngeal samples
 - Area under viral load–time curve (AUEC)
 - Peak viral load
 - Time to resolution of infection
- Duration of hospitalization
- Duration of ICU stay
- Antibiotic usage for respiratory infections
- Complications of influenza:
 - Pneumonia (HAP/VAP)
 - Exacerbations of chronic lung disease
 - Myocarditis
 - Acute respiratory distress syndrome (ARDS)
 - Otitis media
 - Other related complications
- All-cause readmission at Day 30 and Day 60
- Duration of ventilation

Pharmacokinetic Outcome Measures

The primary PK outcome measures for this study are as follows:

- PK parameters for MHAA4549A in serum including total exposure (i.e., AUC), maximum observed concentration (C_{max}), clearance, half-life, and volume of distribution, when appropriate, as data allow

The exploratory PK outcome measures for this study are as follows:

█ [REDACTED]

█ [REDACTED]

Exploratory Outcome Measures

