5.2.2 Serious Adverse Events (Immediately Reportable to the Sponsor)

A serious adverse event is any adverse event that meets any of the following criteria:

- Fatal (i.e., the adverse event actually causes or leads to death)

- Life threatening (i.e., the adverse event, in the view of the investigator, places the patient at immediate risk of death)
 - This does not include any adverse event that had it occurred in a more severe form or was allowed to continue might have caused death.
- Requires or prolongs inpatient hospitalization (see [Section 5.3.5.10](#))
- Results in persistent or significant disability/incapacity (i.e., the adverse event results in substantial disruption of the patient's ability to conduct normal life functions)
- Congenital anomaly/birth defect in a neonate/infant born to a mother exposed to study drug
- Significant medical event in the investigator's judgment (e.g., may jeopardize the patient or may require medical/surgical intervention to prevent one of the outcomes listed above)

The terms "severe" and "serious" are not synonymous. Severity refers to the intensity of an adverse event (e.g., rated as mild, moderate, or severe, or according to Division of AIDS Table for Grading the Severity of Adult and Pediatric Adverse Events (DAIDS); see [Section 5.3.3](#), [Appendix 8](#), and [Appendix 9](#)); the event itself may be of relatively minor medical significance (such as severe headache without any further findings).

Severity and seriousness need to be independently assessed for each adverse event recorded on the eCRF.

Serious adverse events are required to be reported by the investigator to the Sponsor immediately (i.e., no more than 24 hours after learning of the event; see [Section 5.4.2](#) for reporting instructions).

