5.3.3 Assessment of Severity of Adverse Events

Investigators will seek information on adverse events and serious adverse events at each patient contact. All AEs, and SAEs, whether reported by the patient or noted by authorized study personnel, will be recorded.

The adverse event grading (severity) scale in the DAIDS v1.0 will be used for assessing AE severity (see [Table 5](#)).

Table 5 Adverse Event Grading (Severity) Scale

PARAMETER	GRADE 1 MILD	GRADE 2 MODERATE	GRADE 3 SEVERE	GRADE 4 POTENTIALLY LIFE- THREATENING
ESTIMATING SEVERITY GRADE				
Clinical AE NOT identified elsewhere in this DAIDS AE Grading Table	Symptoms causing no or minimal interference with usual social and functional activities	Symptoms causing greater than minimal interference with usual social & functional activities	Symptoms causing inability to perform usual social & functional activities	Symptoms causing inability to perform basic self-care functions OR Medical or operative intervention indicated to prevent permanent impairment, persistent disability, or death

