6.5 SAFETY ANALYSES

The safety analyses will include all randomized patients who received study drug, with patients grouped according to the treatment actually received. Safety parameters to be evaluated include adverse events (including deaths, serious adverse events, discontinuations due to adverse events, and the incidence and severity of adverse events), clinical laboratory tests, vital signs (including SpO₂ measurements), and ECGs.

All collected adverse event data will be listed by study site and patient number. All adverse events that occur on or after treatment on Day 1 will be summarized for each treatment group by mapped term, appropriate thesaurus levels, body system, and event within each body system, and toxicity grade. In addition, all serious adverse events, including deaths, will be listed separately and summarized. SAEs caused by a protocol-mandated intervention (e.g., invasive procedures such as biopsies, discontinuation of medications) that occur between consent and first dose of study medication will be listed separately.

Laboratory data with values outside of the normal ranges will be identified. In addition, select laboratory data will be summarized by treatment group using descriptive summary statistics.

The absolute and percentage changes from baseline in vital sign parameters will be computed, and changes deemed clinically significant by the Investigator will be noted. Appropriate descriptive summary statistics will be provided for all vital sign parameters

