[Redacted]

[Redacted]

[Redacted]

[Redacted]

APPENDIX 6

[REDACTED]

[REDACTED]

[REDACTED]

[REDACTED]

[REDACTED]

APPENDIX 7

SOFA Score Calculation

Administration of MHAA4549A will be performed in a setting with emergency medical equipment and personnel who are trained to monitor for and respond to medical emergencies. A qualified physician will be on site during study drug administration for all patients.

The following equipment is needed in the event of a suspected anaphylactic reaction during study drug infusion:

- Airway management equipment
- O₂
- Epinephrine for subcutaneous, intravenous, and/or endotracheal use in accordance with standard practice
- Antihistamines
- Corticosteroids
- IV infusion solutions, tubing, catheters, and tape

The following are the procedures to follow in the event of a suspected anaphylactic reaction during study drug infusion:

Stop the study drug infusion.

Maintain an adequate airway.

Administer antihistamines, epinephrine, or other medications as required by patient status and directed by the physician in charge.

Continue to observe the patient and document observations.

APPENDIX 8
DAIDS Toxicity Grading Tables for Clinical Abnormalities

**From the FDA Guidance document ‘Toxicity Grading Scale for
Healthy Adult and Adolescent Volunteers Enrolled in
Preventative Vaccine Clinical Trials’ (September 2007)**

Vital Signs ^a	Mild (Grade 1)	Moderate (Grade 2)	Severe (Grade 3)	Potentially Life Threatening (Grade 4)
Fever (°C) ^b (°F)*	38.0 – 38.4 100.4 – 101.1	38.5 – 38.9 101.2 – 102.0	39.0 – 40.0 102.1 – 104.0	>40 >104
Tachycardia – beats per minute	101- 115	116 – 130	>130	ER visit or hospitalization for arrhythmia
Bradycardia – beats per minute ^c	50 – 54	45 – 49	<45	ER visit or hospitalization for arrhythmia
Hypertension (systolic) – mmHg	141 – 150	151 – 155	>155	ER visit or hospitalization for malignant hypertension
Hypertension (diastolic) – mmHg	91 – 95	96 – 100	>100	ER visit or hospitalization for malignant hypertension
Hypotension (systolic) – mmHg	85 – 89	80 – 84	<80	ER visit or hospitalization for hypotensive shock
Respiratory Rate – breaths per minute	17 – 20	21 – 25	>25	Intubation

^a Subject should be at rest for all vital sign measurements.

^b Oral/tympanic temperature; no recent hot or cold beverages or smoking.

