APPENDIX 8 (cont'd)
DAIDS Toxicity Grading Tables for Clinical Abnormalities

Systemic (General)	Mild (Grade 1)	Moderate (Grade 2)	Severe (Grade 3)	Potentially Life Threatening (Grade 4)
Nausea/vomiting	No interference with activity or 1–2 episodes/ 24 hours	Some interference with activity or >2 episodes/ 24 hours	Prevents daily activity, requires outpatient IV hydration	ER visit or hospitalization for hypotensive shock
Diarrhea	2–3 loose stools or <400 g/ 24 hours	4–5 stools or 400–800 g/ 24 hours	5 or more watery stools or >800 g/ 24 hours or requires outpatient IV hydration	ER visit or hospitalization
Headache	No interference with activity	Repeated use of non-narcotic pain reliever >24 hours or some interference with activity	Significant; any use of narcotic pain reliever or prevents daily activity	ER visit or hospitalization
Fatigue	No interference with activity	Some interference with activity	Significant; prevents daily activity	ER visit or hospitalization
Myalgia	No interference with activity	Some interference with activity	Significant; prevents daily activity	ER visit or hospitalization

Systemic Illness	Mild (Grade 1)	Moderate (Grade 2)	Severe (Grade 3)	Potentially Life Threatening (Grade 4)
Illness or clinical adverse event (as defined according to applicable regulations)	No interference with activity	Some interference with activity no requiring medical intervention	Prevents daily activity and requires medical intervention	ER visit or hospitalization

APPENDIX 9

DAIDS Toxicity Grading Tables for Laboratory Abnormalities

Adapted from Division of Microbiology and Infectious Diseases (DMID) Adult Toxicity Table November 2007 DRAFT and FDA Guidance document 'Toxicity Grading Scale from Healthy Adult and Adolescent Volunteers Enrolled in Preventative Vaccine Clinical Trials

Abbreviations used in the table:

█; CPK= creatine phosphokinase; Dec= Decreased; IV= Intravenous; LLN= Lower limit of normal; Mod= Moderate; Req= Required; Rx= Therapy; SGOT= serum glutamic oxaloacetic transaminase; SGPT= serum glutamic pyruvic transaminase; ULN= Upper limit of normal.

HEMATOLOGY				
	Grade 1	Grade 2	Grade 3	Grade 4
Hemoglobin	9.5 – 10.5 g/dL	8.0 – 9.4 g/dL	6.5 – 7.9 g/dL	<6.5 gm/dL
Absolute Neutrophil Count	1,000 – 1,500/mm ³	750 – 999/mm ³	500 – 749/mm ³	<500/mm ³
*Platelets	125,000 – 140,000/mm ³	100,000 – 124,999/mm ³	25,000 – 99,999/mm ³	<25,000/mm ³
WBCs	11,000 – 13,000/mm ³	13,000 – 15,000/mm ³	15,000 – 30,000/mm ³	>30,000 or <1,000/mm ³

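### Adverse event severity is graded under a DAIDS label, but the attached tables come from other scales, and several of their Grade 4 criteria cannot separate severe from mild events in inpatients

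*Combined protocol and SAP*

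**What the plan says.** All references are to the combined protocol and SAP, Version 3 (VHP Only), unless stated.

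- **Section 5.3.3** names the instrument: "The adverse event grading (severity) scale in the DAIDS v1.0 will be used for assessing AE severity". It then prints a single row, Table 5, for clinical events not listed elsewhere. That row grades by loss of function. Hospitalization is not a criterion.
- **Section 5.2.2** refers the rater to Section 5.3.3 and to Appendices 8 and 9 for DAIDS grading. It also requires severity and seriousness to be judged independently for each event, and it lists hospitalization among the seriousness criteria.
- **Appendix 8** is headed "DAIDS Toxicity Grading Tables for Clinical Abnormalities". Directly below, it gives its source as the FDA scale (September 2007) for "Healthy Adult and Adolescent Volunteers Enrolled in" preventive vaccine trials.
- **Appendix 9** carries the DAIDS heading too, but states that it is adapted from a November 2007 DMID draft and the same FDA scale.
- **Appendix 8, Grade 4.** For diarrhea, headache, fatigue, myalgia and the general illness row, the whole criterion is "ER visit or hospitalization". For respiratory rate it is intubation.
- **Section 6.5** summarizes adverse events by arm, by body system "and event within each body system, and toxicity grade".

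**The concern.** Adverse event severity is part of the safety objective (Section 2.1), and grade is one axis of the Section 6.5 tables. Sites are told to use one scale and handed tables taken from others, under the first scale's name. The attached clinical table was written for people living at home, for whom a hospital visit marks a bad outcome. In this trial every patient is already in hospital and some may already be intubated.

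With about 170 centers planned (Section 3.1.1), two raters following the protocol in good faith can give the same event different grades. Event counts can move as well, because Section 5.3.5.3 has a persistent event that becomes more severe recorded as a new event.

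**Working it through.** No power or alpha figure is at stake. The check is a count of the Appendix 8 cells, one product, and a comparison of the two general rules.

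**1. Grade 4 cells in Appendix 8 (13 rows).**

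| Grade 4 criterion | Rows | Count |
|---|---|---|
| ER visit or hospitalization for a named condition | tachycardia, bradycardia, systolic hypertension, diastolic hypertension, hypotension, nausea/vomiting | 6 |
| ER visit or hospitalization, no condition named | diarrhea, headache, fatigue, myalgia, general illness row | 5 |
| Intubation | respiratory rate | 1 |
| Numeric threshold | fever (above 40 °C) | 1 |

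6 + 5 + 1 + 1 = 13. Eleven cells use ER visit or hospitalization. The five without a named condition, plus intubation, are the ones that fail in this population.

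**2. Who already meets the wording.** All patients are hospitalized at entry (Section 4.1.1) and remain so for at least 24 hours after infusion (Section 1.3.2.4). The cap on positive pressure ventilation is 45% of 334 (Section 3.1.1): 0.45 × 334 = 150.3, so about 150 patients at most. Section 3.2.2 counts both mask and intubation as positive pressure ventilation and gives no split. The number intubated at entry can therefore lie anywhere from 0 to about 150.

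**3. The two general rules compared.** Take an event that neither appendix lists.

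- It prolongs the stay, but the patient can still manage basic self-care and needs no intervention to avert lasting harm or death. Table 5 gives Grade 3 at most. The Appendix 8 general row gives Grade 4 if the rater counts a prolonged stay as hospitalization, and a lower grade if not.
- It takes away basic self-care but neither causes nor prolongs admission. Table 5 gives Grade 4. Appendix 8 gives Grade 3 at most if the rater requires the event itself to cause hospitalization.

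The rules can thus disagree in either direction, and no order of precedence is stated.

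**4. Severity and seriousness.** Section 5.2.2 keeps the two apart. The five unqualified cells use a seriousness criterion as the definition of the top severity grade.

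**5. Smaller inconsistencies.**

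- A white cell count of exactly 13,000/mm³ falls in Grades 1 and 2, and exactly 15,000/mm³ in Grades 2 and 3. Five watery stools fit Grades 2 and 3.
- Grade 3 for vomiting and for diarrhea refers to IV hydration as an outpatient, which does not fit an inpatient.
- The synopsis recovery criterion is "Respiratory rate < 24 breaths per minute" off oxygen for at least 24 hours. Appendix 8 puts 17-20 in Grade 1 and 21-25 in Grade 2, so a rate of 17-23 can satisfy the recovery criterion and still fall in a graded band.

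**The case against.** The strongest reply is that an experienced rater will not be misled. In the headache row, hospitalization ordinarily means admission because of the headache. Section 5.3.5.10 treats the index stay separately from later or prolonged hospitalization, although it governs seriousness and not grading. A reader might infer that every in-hospital headache becomes Grade 4; the documents do not force that reading. What remains is that, on the ordinary reading, Grade 4 in these five rows is hard to reach during the index stay, and Table 5 still offers a different rule for unlisted events.

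Second, being in hospital or on a ventilator at entry does not itself create a graded event. Before dosing, only serious events caused by protocol procedures are reported (Section 5.3.1). Pre-existing conditions count only if they worsen (5.3.5.8), expected influenza deterioration only if it worsens unexpectedly or changes in nature (5.3.5.9), and an abnormal vital sign is not automatically an event (5.3.5.5). This stands. The figure of 150 is a cap on ventilated patients, not a count of Grade 4 events or of intubated patients.

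Third, much of the grading still works. Six hospitalization cells name a condition that an influenza admission does not meet. Fever, the numeric vital-sign bands and most laboratory grades can be applied. The respiratory-rate comparison is weak, because a recovery threshold is not a definition of normal and it is one of five criteria of which three must be met.

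Fourth, sites are blinded and randomization is 1:1, stratified by ventilation status (Section 4.2), so the noise should fall largely equally on the arms. Section 6.5 also reports deaths, serious events, discontinuations, laboratory values and changes in vital signs.

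**Conclusion.** The point holds as a mislabelled and internally inconsistent grading system. One name covers material from several sources, two general rules compete without precedence, and six of the 13 Appendix 8 rows have a Grade 4 criterion that cannot reliably separate severe from mild events in these inpatients. The likely result is rater-dependent noise and a distorted absolute Grade 3-4 distribution. The size of that distortion cannot be computed, because neither the intubated share nor the expected event rates are given.

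Two stronger conclusions are tempting. A reader might infer that severity grades as a whole are uninterpretable, or that any drug-related difference would be masked. The documents support neither: the numeric criteria survive, baseline findings are filtered, and blinded grading on a common scale points to dilution, not to bias between arms.

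The conclusion rests on Version 3. Versions 1 and 2 carry the same Appendix 8 tables. Version 5 (Global) adds a third arm but is represented only by its title page and part of its amendment rationale, so whether its appendices, or the 334, 45% and 170-center figures, still apply cannot be checked here.

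**What to change.** 1. Reconcile Section 5.3.3, Table 5 and Appendices 8 and 9 to one named scale: either attach the scale that Section 5.3.3 names, or name in Section 5.3.3 the scale that is attached.
2. If the attached tables are kept, state that for events during the index stay the functional Grade 4 wording of Table 5 takes precedence over the five unqualified hospitalization cells and over intubation.
3. Make the overlapping bands mutually exclusive (white cell count at 13,000 and 15,000/mm³; five stools).
4. Confirm whether the Version 5 appendices carry the same tables, and apply the correction there if they do.

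The cost is a corrected or replaced appendix and a sentence or two in Section 5.3.3. Treatment, visits and sample size are unchanged. The one small loss is that grades become less directly comparable with any earlier study that used the volunteer scale.

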APPENDIX 8 (cont'd)
DAIDS Toxicity Grading Tables for Clinical Abnormalities

Systemic (General)	Mild (Grade 1)	Moderate (Grade 2)	Severe (Grade 3)	Potentially Life Threatening (Grade 4)
Nausea/vomiting	No interference with activity or 1–2 episodes/ 24 hours	Some interference with activity or >2 episodes/ 24 hours	Prevents daily activity, requires outpatient IV hydration	ER visit or hospitalization for hypotensive shock
Diarrhea	2–3 loose stools or <400 g/ 24 hours	4–5 stools or 400–800 g/ 24 hours	5 or more watery stools or >800 g/ 24 hours or requires outpatient IV hydration	ER visit or hospitalization
Headache	No interference with activity	Repeated use of non-narcotic pain reliever >24 hours or some interference with activity	Significant; any use of narcotic pain reliever or prevents daily activity	ER visit or hospitalization
Fatigue	No interference with activity	Some interference with activity	Significant; prevents daily activity	ER visit or hospitalization
Myalgia	No interference with activity	Some interference with activity	Significant; prevents daily activity	ER visit or hospitalization

Systemic Illness	Mild (Grade 1)	Moderate (Grade 2)	Severe (Grade 3)	Potentially Life Threatening (Grade 4)
Illness or clinical adverse event (as defined according to applicable regulations)	No interference with activity	Some interference with activity no requiring medical intervention	Prevents daily activity and requires medical intervention	ER visit or hospitalization

APPENDIX 9

DAIDS Toxicity Grading Tables for Laboratory Abnormalities

Adapted from Division of Microbiology and Infectious Diseases (DMID) Adult Toxicity Table November 2007 DRAFT and FDA Guidance document 'Toxicity Grading Scale from Healthy Adult and Adolescent Volunteers Enrolled in Preventative Vaccine Clinical Trials

Abbreviations used in the table:

█; CPK= creatine phosphokinase; Dec= Decreased; IV= Intravenous; LLN= Lower limit of normal; Mod= Moderate; Req= Required; Rx= Therapy; SGOT= serum glutamic oxaloacetic transaminase; SGPT= serum glutamic pyruvic transaminase; ULN= Upper limit of normal.

HEMATOLOGY				
	Grade 1	Grade 2	Grade 3	Grade 4
Hemoglobin	9.5 – 10.5 g/dL	8.0 – 9.4 g/dL	6.5 – 7.9 g/dL	<6.5 gm/dL
Absolute Neutrophil Count	1,000 – 1,500/mm ³	750 – 999/mm ³	500 – 749/mm ³	<500/mm ³
*Platelets	125,000 – 140,000/mm ³	100,000 – 124,999/mm ³	25,000 – 99,999/mm ³	<25,000/mm ³
WBCs	11,000 – 13,000/mm ³	13,000 – 15,000/mm ³	15,000 – 30,000/mm ³	>30,000 or <1,000/mm ³
*Lymphocytes Decrease – cell/mm ³	750 – 1,000	500 – 749	250 – 499	<250
*Eosinophils – cell/mm ³	650 – 1500	1501 – 5000	>5000	Hypereosinophilic
Abnormal Fibrinogen	Low: 100 – 200 mg/dL High: 400 – 600 mg/dL	Low: <100 mg/dL High: >600 mg/dL	Low: <50 mg/dL	Fibrinogen associated with gross bleeding or with disseminated coagulation
Fibrin Split Product	20 – 40 mcg/mL	41 – 50 mcg/mL	51 – 60 mcg/mL	>60 mcg/mL
Prothrombin Time (PT)	1.01 – 1.25 x ULN	1.26 – 1.50 x ULN	1.51 – 3.0 x ULN	>3 x ULN
Activated Partial Thromboplastin Time (APTT)	1.01 – 1.66 x ULN	1.67 – 2.33 x ULN	2.34 – 3 x ULN	>3 x ULN
Methemoglobin	5.0 – 9.9%	10.0 – 14.9%	15.0 – 19.9%	>20.0%

From the FDA Guidance document 'Toxicity Grading Scale from Healthy Adult and Adolescent Volunteers Enrolled in Preventative Vaccine Clinical Trials'

